Previous studies observed alleviation of neuropathic symptoms after a relatively short treatment period (Hidmark et al., 2017; Humpert et al., 2009; Kempf & Martin, 2010; Reichstein et al., 2005). However, most of these studies had no control group and therefore, the data on the effect of high tone therapy is weak.

Therefore, the treatment phase in our study will last three weeks. One treatment session will take about 60min. The minimum number of treatment sessions to be completed will be 5 out of 7 days. The device saves minutes of treatment and therefore offers the clinician to monitor the participants' compliance. Therefore, the treatment will be home-based.

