## **Assessments**

Assessments will be carried out at the following points of time: Baseline, after the first treatment week, at the end of the treatment phase and follow up after two weeks.

After completing the follow-up assessment, the participants will be unblinded and subjects of the placebo group will be offered to join the treatment group (opt in).

The baseline assessment includes a test of vibration sensation by using a clanging tuning fork (Panosyan et al., 2016). In this examination, certain anatomical localizations will be touched with the tuning fork (i.e., the dorsum of the interphalangeal joint of the hallux and the medial malleolus). Several studies reported that this test not only detects peripheral neuropathy accurately but also that it is superior to the monofilament test (Meijer et al., 2005; Oyer et al., 2007). Moreover, normative values for several age groups have been published (Martina et al., 1998).

In addition, full medical and social history will be collected, including:

- demographic data (date of birth, height, weight)
- previous conditions and operations
- course and treatment of the current cancer, duration of neuropathy
- (pain) medication (patients will be required not to change their medication during the study)
- Walking aids
- Need for social / nurse support (type of support and hours per week)
- Social history (profession, level of education, family status)

The following outcome parameters will be determined and quantified as part of all assessments:

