## **Objectives**

The primary objective is to compare the changes in intensity of paresthesias between the two patient groups. This will be performed via standardized questionnaires with numeric rating scales (NRS) in the baseline assessment, after the first treatment week, at the end of the treatment phase and follow up after two weeks.

The secondary objective is to evaluate neuropathic symptoms further in detail and to assess quality of life via standardized questionnaires with NRS as well as via internationally accepted questionnaires.

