## **Hypothesis**

We hypothesize that high tone therapy will bring about a significantly stronger reduction in neuropathic symptoms, compared to the placebo treatment.

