## **Statistical analysis**

To show that the primary objective, changes in intensity of paresthesias measured with the numeric rating scale, will bring about a significantly stronger reduction in the intervention group, a repeated measures analysis of variance will be conducted. A mean value out of 8 questions will be calculated which will be compared between the intervention group and the placebo group (between-subject-factor) and between 4 measurements (within-subject-factor). A 4\*2 within-between-interaction can point out differences in intensity of paresthesias between all times of measurements and between both groups. In a two-sided test the alpha level will be set at 0.05 to show significant effects.

Also, the secondary objectives, measured with standardized questionnaires, will be analysed in a repeated measures analysis of variance model, since all questionnaires will be tested at 4 times of measurement. With the EORTC QLQ-C30 (3rd version) a global health status, functional scales and symptom scales are calculated. With the EORTC QLQ-CIPN20 moreover a sensory scale, a motor scale and an autonomic scale are calculated. Since all subscales of both questionnaires are metric, a multivariate model can be calculated via repeated measures analysis of variance (alpha 0.05, two-sided)

In addition, a neuropathic-symptom-score (NSS) with 5 more questions is calculated. At a range of 0-10 points patients can be classified in 4 groups (<3 points, 3-5 points, 6-8 points, 9-10 points) and a Chi-square analysis can show differences in frequencies

at 4 times of measurement (alpha 0.05). Under the assumption of a normal distribution of the residuals and homoscedasticity the 4 classified groups of the NSS questionnaire could be used to build an additional factor and show differences in a repeated measures ANOVA between the 4 groups (additional between-subject-factor) in the primary objective and the secondary objective model (alpha 0.05, two-sided)

Logistic-Regression models could show combined effects of primary and secondary objectives, if the quality of data is sufficient (alpha 0.05). If the quality of data is insufficient simple effects between primary and secondary objectives, and all subscales of the secondary objectives questionnaires, could be shown with Pearson correlations (alpha 0.05, two-sided).

Descriptive statistics and frequencies will be calculated for sampling variables.

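### The primary test is a 3-df group-by-time interaction with no primary visit or contrast, so a significant result does not by itself show a stronger reduction with treatment

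*Protocol*

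**What the plan says.** The Hypothesis section is directional: "high tone therapy will bring about a significantly stronger reduction in neuropathic symptoms, compared to the placebo treatment". The Statistical analysis section repeats that aim for the primary objective. It says that, to show that the change in paresthesia intensity "will bring about a significantly stronger reduction in the intervention group, a repeated measures analysis of variance will be conducted".

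The model has two groups (between-subject) and four measurements (within-subject). The only effect named for the primary objective is the 4-by-2 interaction, which "within-between-interaction can point out differences in intensity of paresthesias between all times of measurements and between both groups". The level follows: "In a two-sided test the alpha level will be set at 0.05 to show significant effects".

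The Assessments section gives the visits as "Baseline, after the first treatment week, at the end of the treatment phase and follow up after two weeks". The Objectives section lists the same four: "in the baseline assessment, after the first treatment week, at the end of the treatment phase and follow up after two weeks". Neither section ranks them. The Treatment section states that "the treatment phase in our study will last three weeks", so the fourth measurement is taken off treatment. No primary visit, contrast or follow-up comparison is named anywhere in the protocol.

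**The concern.** The protocol states both the conclusion it wants (a stronger reduction with treatment) and the test meant to deliver it (the interaction). The conclusion does not follow from the test. The interaction F asks whether the two mean profiles over four visits are parallel. Any departure makes it significant: a benefit, a harm, a difference that has gone by end of treatment, or one that appears only after treatment has stopped.

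Every two-sided test also rejects for harm, so that alone is no fault. The difference is that a single 1-df contrast comes with one signed estimate at a stated time, and this answers the hypothesis. The omnibus F has no such estimate. After a significant result, someone must still choose which visit or comparison supports the claim, and the protocol leaves that choice open until the data are seen.

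A second, lesser point is efficiency. Three degrees of freedom are spent on all shapes of difference, and for some plausible time courses this costs power.

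**Working it through.** **Plan's own figure.** There is none to reproduce: the protocol shown gives no sample size, power, effect size, SD or correlation.

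**Inputs from the protocol.** Two groups, four measurements, two-sided alpha 0.05. Interaction df = (4 − 1)(2 − 1) = 3.

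**Assumed inputs.** n = 40 per arm (also 30 and 60); full effect 0.6 SD; compound symmetry with correlation ρ = 0.3, 0.5, 0.7. d_t is the group difference at visit t in SD units, with visits in the order baseline, week 1, end of treatment, follow-up.

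**Noncentrality and df (F tests)**

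- Omnibus interaction: (n/2) Σ(d_t − d̄)² / (1 − ρ); df 3 and 3(2n − 2)
- Unadjusted change to end of treatment: (n/2) d₃² / [2(1 − ρ)]; df 1 and 2n − 2
- Baseline-adjusted end of treatment: (n/2) d₃² / (1 − ρ²); df 1 and 2n − 3
- Baseline-adjusted mean m of the three post-baseline visits: (n/2) m² / [(1 + 2ρ)/3 − ρ²]; df 1 and 2n − 3

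**Step 1: the omnibus test does not separate the patterns.** For sustained benefit (0, 0.6, 0.6, 0.6), d̄ = 0.45 and Σ(d_t − d̄)² = 0.45² + 3 × 0.15² = 0.27. Sustained harm has the same sum. For week 1 only (0, 0.6, 0, 0) or follow-up only (0, 0, 0, 0.6), d̄ = 0.15 and the sum is 0.45² + 3 × 0.15² = 0.27 again. At ρ = 0.5 the noncentrality is 20 × 0.27 / 0.5 = 10.8 in all four cases, with rejection probability 0.788.

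| Pattern (n = 40; ρ 0.3 / 0.5 / 0.7) | Omnibus | Adjusted end of treatment | Adjusted post-baseline mean |
|---|---|---|---|
| Sustained benefit or sustained harm | 63 / 79 / 96% | 79 / 86 / 96% | 98 / 98 / 99.7% |
| Week 1 only, or follow-up only | 63 / 79 / 96% | 5 / 5 / 5% | 26 / 28 / 36% |

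The exact equality of the omnibus column comes from choosing shapes with equal sums of squares. The lack of sign and visit does not depend on that choice.

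**Step 2: power when the effect is half-size at week 1 and follow-up (0, 0.3, 0.6, 0.3).** Σ(d_t − d̄)² = 0.18. At ρ = 0.5 the omnibus noncentrality is 20 × 0.18 / 0.5 = 7.2 on 3 df. The unadjusted change has 20 × 0.36 / 1 = 7.2 on 1 df, and the adjusted contrast has 20 × 0.36 / 0.75 = 9.6 on 1 df.

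| Test (n = 40; ρ 0.3 / 0.5 / 0.7) | Power |
|---|---|
| Omnibus | 45 / 60 / 83% |
| Unadjusted change to end of treatment | 61 / 76 / 93% |
| Baseline-adjusted end of treatment | 79 / 86 / 96% |
| Baseline-adjusted post-baseline mean | 76 / 78 / 89% |

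At ρ = 0.5, the move from 0.595 to 0.755 (16 points) comes from choosing one visit. The move from 0.755 to 0.864 (11 points) comes from the baseline covariate. Omnibus against adjusted end of treatment for the same pattern:

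- 30 per arm: 34 / 46 / 70% against 67 / 75 / 89%
- 60 per arm: 63 / 79 / 96% against 93 / 96 / 99.5%

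**Step 3: patterns that favour the omnibus test.** For a sustained effect the unadjusted change has 61 / 76 / 93%, so the omnibus test (63 / 79 / 96%) loses nothing against it. If the effect keeps growing after treatment (0, 0.2, 0.4, 0.6; ρ = 0.5), the omnibus test has 65%, the adjusted end-of-treatment contrast 53% and the adjusted post-baseline mean 78%.

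**Step 4: checks.** Simulation (8,000 runs, n = 40, ρ = 0.5) gave, for omnibus / adjusted end of treatment / adjusted mean:

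- null: 0.050 / 0.050 / 0.051
- half-size pattern: 0.595 / 0.857 / 0.774
- sustained: 0.779 / 0.863 / 0.984
- week 1 only: 0.789 / 0.054 / 0.277
- follow-up only: 0.787 / 0.049 / 0.276

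A separate calculation with 50 per arm, SD 2, a 1-point effect and ρ = 0.5 agrees. The omnibus test rejects in 0.68 of trials for benefit (0, −0.5, −1, −1) and in the same 0.68 for its mirror-image harm. It rejects in 0.72 for a 1-point difference at week 1 only or at follow-up only. In those single-visit cases, about 3% of the significant trials also show a significant end-of-treatment benefit.

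**The case against.** Planned contrasts that break down an interaction are commonly left to a statistical analysis plan, which may exist. The protocol says only that the interaction can point out differences and never calls it the sole criterion of success. The objective is to compare changes over four visits, and an interaction does test equality of change profiles. In practice the F is read beside the group means: in a simulation of benefit patterns (40 per arm, ρ = 0.5), the mean post-baseline change favoured treatment in over 99% of significant tests. The power argument rests on assumed inputs, part of the gain is due to the covariate, and for a growing effect the omnibus test beats the end-of-treatment contrast.

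Much of this stands as a limit on the point. The F test holds its 5% level under its assumptions, and no inflation is claimed. A true sustained harm would be visible in the means, so the practical gap is mainly which visit counts. The power loss depends on the time course. The post-baseline mean does not say when the groups differ either, although it gives one signed estimate of the whole course.

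The objection does not remove the main point. The interaction is the only effect the protocol names for the primary objective. The group main effect would average in the pre-treatment baseline and so would not test change. The protocol itself ties a directional conclusion to a test without direction or visit. A later plan could add contrasts, but the objective and test set here would still not say which one decides.

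**Conclusion.** The concern holds. The test named for the primary objective has 3 df, no sign and no visit, while the hypothesis is a stronger reduction with treatment. That part needs no assumed number.

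The size does need assumptions (no N, SD or correlation is given). With 40 per arm, 0.6 SD, compound symmetry and ρ 0.3 / 0.5 / 0.7, the test is significant in 63 / 79 / 96% of trials when the groups differ only at week 1 or only after treatment stops, exactly as often as for sustained benefit. The power cost ranges from substantial in the half-size pattern to none against unadjusted change for a sustained effect. It reverses against the end-of-treatment contrast for an effect that grows after treatment. This should be fixed, mainly for interpretation and only secondarily for power.

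**What to change.** Replace the interaction as primary test by one pre-specified 1-df contrast at two-sided alpha 0.05, reported with its estimate and 95% CI. Two forms fit the protocol:

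- the baseline-adjusted group difference in the paresthesia score at the end of the three-week treatment phase; or
- if the sponsor means the whole course, as the Objectives section can be read, the baseline-adjusted group difference in the mean of the three post-baseline visits.

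The choice is the sponsor's and should be fixed before any unblinded data are seen. The interaction and the remaining visits stay as secondary analyses.

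The cost is wording in the protocol and analysis plan, because all the measurements are already scheduled. The drawback is that a difference seen mainly at a visit outside the chosen contrast would no longer count as primary success. If an effect that grows after treatment is thought likely, the post-baseline mean is the safer of the two.

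### The NSS Chi-square names no arm comparison, and on either plausible layout it is a worse test of the between-arm hypothesis than the uncut score adjusted for baseline

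*Protocol*

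**What the plan says.** Under Statistical analysis, the NSS is described thus: "At a range of 0-10 points patients can be classified in 4 groups" (below 3, 3-5, 6-8 and 9-10 points). Then "a Chi-square analysis can show differences in frequencies" "at 4 times of measurement (alpha 0.05"). No arm is mentioned in that sentence.

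The same section is explicit for the primary outcome: a mean paresthesia value "which will be compared between the intervention group and the placebo group (between-subject-factor"), with the four measurements as the within-subject factor. The Hypothesis section expects a "significantly stronger reduction in neuropathic symptoms, compared to the placebo treatment".

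Two further statements bear on the NSS. The secondary objectives in general "will be analysed in a repeated measures analysis of variance model, since all questionnaires will be tested at 4 times of measurement", which may or may not include the NSS score. And "the 4 classified groups of the NSS questionnaire could be used to build an additional factor" in the primary and secondary models, with no visit named for the class. According to Assessments, the NSS is collected from the same patients at baseline, after week 1, at the end of treatment and at follow-up.

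**The concern.** The Chi-square is the only analysis that the protocol spells out for the NSS, and it has its own alpha. The trial's question is whether the active arm improves more than placebo. A reader cannot tell from the sentence which table is to be tested, and the two plausible tables answer different questions.

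A class-by-time table asks whether the class distribution changes over visits. It would react to improvement shared by both arms, which is plausible in a placebo-controlled symptom trial, and respond poorly to improvement in the active arm alone. An arm-by-class table at each visit asks the right question, but four times over without adjustment, once before any treatment. It also treats ordered classes as unordered and makes no use of the baseline score. At stake is whether the NSS result can be interpreted as evidence on the hypothesis, and how much of its information is used.

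**Working it through.** **Inputs from the protocol.** Four classes with the cut points above; four assessments of the same patients; alpha 0.05. No sample size, SD, correlation or NSS effect is stated, so there is no planned figure to reproduce.

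**Assumptions.** 30 or 40 patients per arm; NSS mean 6, SD 2, rounded and limited to 0-10; equal within-patient correlation of 0.3, 0.5 or 0.7 between visits; improvement, where present, of 0.6 SD (0.6 × 2 = 1.2 points), half reached at week 1 and all of it at end of treatment and follow-up. Simulation with 3,000 to 5,000 runs per setting. Ranges below run over the three correlations.

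**Layout 1: class by time, arms pooled.** Pearson's statistic Σ(O−E)²/E on 4 × 4 cells has (4−1)(4−1) = 9 degrees of freedom and assumes independent observations, whereas each patient contributes four.

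| True state | Rejects, 30 per arm | Rejects, 40 per arm |
|---|---|---|
| No change in either arm | 0.3-3.0% | 0.3-2.8% |
| Both arms improve equally (no treatment effect) | 53-63% | 79-82% |
| Active arm alone improves | 3-11% | 6-16% |

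Ignoring the dependence makes this test conservative. The larger problem is the ordering of the last two rows: it rejects most often when the arms do not differ.

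**Layout 2: arm by class, one table per visit.** Each table is 2 × 4 with (2−1)(4−1) = 3 degrees of freedom and one observation per patient. With no effect, the test at end of treatment rejects in 3.5-4.3%, so it is valid singly. For four independent tests at exactly 5%, the chance of at least one false positive would be 1 − 0.95⁴ = 18.5%. With correlated visits and a slightly conservative test, the simulation gives 13-16% over four visits and 10-12% over the three post-baseline visits.

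Power at end of treatment for a 0.6 SD difference between arms:

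| Analysis | 30 per arm | 40 per arm |
|---|---|---|
| Chi-square, four classes | 33-35% | 47-48% |
| Rank test, same four classes | 53-55% | 66-68% |
| t-test, uncut score | 61-63% | 74-75% |
| Score adjusted for baseline | 64-87% | 78-95% |

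Ignoring class order costs 18-20 percentage points (for example 53.1 − 33.4 = 19.7). Cutting the score costs a further 7-9 (61.2 − 53.1 = 8.1). The gain from baseline adjustment grows with the within-patient correlation. A baseline mean of 5 or 7 leaves the pattern unchanged (Chi-square 34-37% and 45-48%; t-test 60-63% and 73-76%). Repeat simulations under the main assumptions gave 33-49% for the Chi-square and 60-75% for the uncut score.

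**Optional class factor.** Take a true paresthesia effect of −0.60 SD and an NSS-paresthesia correlation of 0.4-0.8. Adding the baseline class leaves the estimate at −0.59 to −0.61. Adding the end-of-treatment class gives −0.49 to −0.56 if treatment shifts the NSS by 0.3 SD, −0.40 to −0.52 if by 0.6 SD, and no change if it does not shift the NSS. Only the choice of visit matters.

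**The case against.** The strongest reply is that the class-by-time reading is not the best one. The section marks compared factors with the word between, and refers to the four times of measurement elsewhere simply to say when questionnaires are given. In a placebo-controlled trial, a comparison of arms at each visit is then the natural sense. This stands in part. A reader might infer that the protocol, as written, treats repeated measurements as independent; the wording does not establish that, because it equally allows a valid table per visit. A reader might also infer an inflated type I error from stacking all visits in one arm-by-class table (12-29% under the same assumptions). No text describes such a table, so that figure should not be held against the plan.

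Second, the general repeated measures ANOVA sentence may already cover the NSS score, which would make the Chi-square a supplement. That is possible. The sentence that follows on subscales refers only to the two EORTC questionnaires, so the point is not settled, and the Chi-square would remain a weak test either way.

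Third, table layout and multiplicity are commonly left to the SAP, which is not at hand. But the protocol is not silent here: it names a test, its classes and an alpha, and on both plausible layouts that choice is worse than an available alternative.

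Fourth, a reader might infer that the NSS-class factor endangers the primary analysis. The documents do not support this. The factor is optional, a between-subject factor takes one value per patient, the baseline class is the obvious choice, and nothing proposes a post-baseline class.

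Finally, simply naming the arms would remove the ambiguity. True, but it would leave four unadjusted tests and the loss of power.

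**Conclusion.** The point holds, with modest severity. The NSS Chi-square leaves its comparison unstated. Read as class by time, it does not test the trial's hypothesis. Read as arm by class per visit, it is valid singly, but it carries about a 13-16% chance of at least one false positive over four visits and has end-of-treatment power of about 33-49%, against about 60-75% for the uncut score and 64-95% with baseline adjustment. All of these sizes rest on assumed sample size, score distribution, correlation and, for power, effect; the ordering of the methods did not change across the settings tried. The finding concerns a secondary outcome, possibly supplementary to the general ANOVA. The 4*2 primary model is unaffected. The class factor needs only a minor clarification.

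**What to change.** Replace the Chi-square sentence with wording to this effect: the NSS 0-10 score will be compared between the intervention and placebo arms in a repeated-measures model of the post-baseline scores, adjusted for baseline NSS, with one named main time point (for example the end of the treatment phase); NSS class frequencies will be reported descriptively by arm and visit.

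If a test of the classes is wanted, use an ordinal between-arm model at that time point, adjusted for baseline, instead of a nominal Chi-square. As a clarification, add that if the optional NSS-class factor is used in the primary or secondary models, it is defined by the baseline class only.

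The cost is wording: the score is already collected at every assessment. The small downside is that the Chi-square loses its inferential role.

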### **Pain and sensory disturbances**

- Numeric rating scale (NRS, 0-10): Paresthesia intensity, mental stress due to paraesthesia, pain intensity, mental stress due to pain, tightness/pressure intensity and mental stress due to tightness/pressure
- European Organisation for Research and Treatment of Cancer Chemotherapy-Induced Peripheral Neuropathy 20 questionnaire (EORTC CIPN 20): This is an international questionnaire to assess chemotherapy induced neuropathy with a

sensory scale, motor scale as well as an autonomic scale (Postma et al., 2005). The CIPN 20 questionnaire has been used in recent studies (Coyne et al., 2013; Gewandter et al., 2018).

- Neuropathy Symptom Score (NSS): This validated questionnaire assesses and quantifies neuropathic symptoms and has been used in recent studies (Hidmark et al., 2017; Jende et al., 2018; Mao et al., 2018).

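### Does offering the NSS classes as an extra between-subject factor condition the arm comparison on a post-randomisation response?

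*Protocol*

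**What the plan says.** The Assessments section sets four visits: "Baseline, after the first treatment week, at the end of the treatment phase and follow up after two weeks". It introduces its list of measures with "The following outcome parameters will be determined and quantified as part of all assessments". The NSS is on that list, under Pain and sensory disturbances, where the protocol says of it: "This validated questionnaire assesses and quantifies neuropathic symptoms and has been used in recent studies".

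The Statistical analysis section uses the NSS in two ways. As an outcome, "patients can be classified in 4 groups (<3 points, 3-5 points, 6-8 points, 9-10 points"), and a chi-square analysis compares class frequencies at the four visits. As an explanatory variable, it is offered conditionally, provided that residuals are normal and variances equal: "the 4 classified groups of the NSS questionnaire could be used to build an additional factor and show differences in a repeated measures ANOVA". The factor is described as an "additional between-subject-factor) in the primary objective and the secondary objective model". No visit is named for this second use.

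The primary analysis comes earlier in the same section: a repeated measures ANOVA with arm (2) between subjects and time (4) within subjects, judged by their interaction at a two-sided 0.05. NSS class is not part of it.

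**The concern.** Three of the four NSS measurements are made after randomisation, and the NSS measures the kind of symptom that the device is expected to relieve. The sentence just before the proposed factor treats the class as something that can differ from visit to visit, whereas a between-subject factor must be constant within a patient. The two uses fit together only if one visit is chosen. The only conditions attached, normal residuals and equal variances, have no bearing on that choice.

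If the class came from week 1, end of treatment or follow-up, the model would compare arms among patients matched on a response to treatment. Randomisation would no longer protect the comparison. Part of a real effect could be adjusted away, or an effect could appear where none exists. The text attaches a 0.05 level and names the primary model, so at first sight the main result seems exposed.

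**Working it through.** **No plan figure to reproduce.** The protocol gives no effect size, standard deviation or correlation for these measures. Only the class cut-points below come from it; every other input is an assumption.

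**Inputs.**
- From the protocol: NSS range 0-10, with classes below 3, 3-5, 6-8 and 9-10.
- Assumed: SD 2 for both the paresthesia rating (NRS) and the NSS; NRS means 5.5 at baseline and 5 at end of treatment; NSS means 6 and 5.5; true arm effect on NRS -1.0; arm effect on NSS -0.5, -1.0 or -2.0; same-visit NRS-NSS correlation ρ of 0.3, 0.5 or 0.7; between-visit correlation r of 0.5 or 0.7; correlation across both measure and visit ρ × r.
- 400,000 simulated patients per scenario.

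**Model.** Change in NRS = β0 + β1 × arm + class terms + error, fitted with no class, with baseline class and with end-of-treatment class. This simplifies the four-visit ANOVA to two visits and main effects.

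**Result with no class or baseline class.** β1 lies between -0.99 and -1.01 in every scenario. Baseline NSS is independent of arm by randomisation, so adjusting for it cannot bias the arm effect here.

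**Result with end-of-treatment class (β1):**

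| r | ρ | NSS effect -0.5 | NSS effect -1.0 | NSS effect -2.0 |
|---|---|---|---|---|
| 0.5 | 0.3 | -0.95 | -0.88 | -0.76 |
| 0.5 | 0.5 | -0.90 | -0.79 | -0.60 |
| 0.5 | 0.7 | -0.85 | -0.71 | -0.41 |
| 0.7 | 0.3 | -0.97 | -0.93 | -0.85 |
| 0.7 | 0.5 | -0.93 | -0.87 | -0.74 |
| 0.7 | 0.7 | -0.90 | -0.83 | -0.65 |

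The loss relative to -1.0 runs from 1 - 0.97 = 3% to 1 - 0.41 = 59%.

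**With no true NRS effect**, an NSS effect of -1.0 and r = 0.5, the end-of-treatment class gives a spurious β1 of +0.12, +0.21 and +0.30 for ρ = 0.3, 0.5 and 0.7. The baseline class gives about 0.

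**Algebraic check.** With equal SDs, the within-arm slope of NRS change on end-of-treatment NSS is ρ - ρr = ρ(1 - r). Adjusting for the continuous score would therefore move β1 upwards by ρ(1 - r) × |NSS effect|.
- Smallest case: 0.3 × 0.3 × 0.5 = 0.045, so β1 = -0.955 (simulated with classes: -0.97).
- Largest case: 0.7 × 0.5 × 2.0 = 0.70, so β1 = -0.30 (simulated with classes: -0.41).

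Four coarse classes carry less information than the score, so they shift the estimate somewhat less, as the simulation shows.

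**What the check settles.** The mechanism is real, but it operates only when a post-baseline NSS defines the class. Whether that applies depends on the text. There, the factor is optional, its visit is unstated, and it is called a between-subject factor, so each patient must have one fixed class. The reference to four times of measurement belongs to the chi-square comparison of frequencies, not to the factor.

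**The case for a change.** The strongest case for a change is that the sentence goes beyond leaving something out. It takes a class just described as varying over four visits, uses it as fixed, names the primary model as its home and gives it a significance level. Read literally, it would permit a biased model and leave the choice of visit open until data are in hand. Naming baseline would take a few words, and baseline NSS is already collected.

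Part of this stands. The visit is unnamed, and a post-baseline class would be a mistake. The rest does not carry. The wording permits an analysis rather than committing to one, and nothing says that it replaces the arm-by-time result. Its stated aim is to show differences between the NSS classes, not to give an adjusted estimate of the arm effect. The statistical analysis plan is not shown, and fixing the visit for a supplementary factor is ordinary work for that document. Barring post-baseline NSS from every model of treatment effect would also go too far, because the NSS is itself an outcome and is to be analysed at all four visits.

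**Conclusion.** The concern does not call for a change. It describes a genuine error that an analyst could make, but the protocol does not prescribe it. The primary arm-by-time ANOVA excludes NSS class and is unaffected whichever visit is chosen. For the optional model, a baseline class is the natural reading and leaves the arm effect unbiased (about -1.0 against a true -1.0). The 3% to 59% shrinkage needs an end-of-treatment class and rests on assumed effects, SDs and correlations in a two-visit simplification. It illustrates the mechanism and does not measure a defect in this plan. What is left is a small gap that analysts fill sensibly. The assessment would differ if a plan or report took the class from a post-baseline visit and presented that model as the test of the device.
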